11.4.1.2. Secondary Efficacy Analyses

11.4.1.2.1. Analyses of ORR in the Other Dose Levels of Part 1 and Part 2b

The same analyses as described in the primary efficacy analyses (Section 11.4.1.1) will be performed by dose group for subjects from Part 1 and for Part 2b as part of the Response Evaluable Set.

11.4.1.2.2. Other Secondary Efficacy Analyses

The secondary efficacy endpoints include duration of response, best percent change in the SLD of measurable tumors, DCR, (the proportion of subjects who achieved a best overall response of CR or PR or stable disease [SD]), CBR (the proportion of subjects who achieved a best overall response of CR or PR or more than 6 months SD), PFS, OS, and ORR assessed by the investigator based on RECIST version 1.1.

Duration of response is defined as the time from the date of the first documentation of objective response (CR or PR) to the date of the first documentation of PD or death due to any cause. Duration of response will be measured for responding subjects (CR or PR) only. Detailed censoring rules for duration of response will be specified in the statistical analysis plan (SAP).

PFS is defined as the time from the date of randomization/registration to the earlier of the dates of the first objective documentation of radiographic PD via independent radiologic facility review based on RECIST version 1.1 or death due to any cause. Detailed censoring rules for PFS will be specified in the SAP.

OS is defined as the time from the date of randomization/registration to the date of death for any cause. If there is no death reported for a subject before the data cut-off for OS analysis, OS will be censored at the last contact date at which the subject is known to be alive.

Duration of response, PFS, and OS will be summarized with median event times and their 2-sided 95% CI for the median using Brookmeyer and Crowley methods for each part/dose group.

Descriptive statistics for the best (minimum) percent change from baseline in the SLD will be provided by part/dose group.

DCR, CBR, ORR assessed by the investigator based on RECIST version 1.1 will be analyzed for each part/dose group in the same manner as the primary ORR analysis.

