5.7.4. Subject Replacement

Subjects that have been enrolled and administered study medication will not be replaced. However, it is allowable to replace a subject that was enrolled but was not administered any study medication.

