6.3. Randomization

For the PK Stage of Part 1, eligible subjects will be randomized by the IXRS in a 1:1:1 ratio into 1 of 3 initial treatment groups: 5.4 mg/kg, 6.4 mg/kg, and 7.4mg/kg.

For the Dose Finding Stage of Part 1, an additional of approximately 30 subjects per dose will be randomized by the IXRS in a 1:1 ratio into 1 of 2 treatment groups selected after the PK Stage.

Randomization will be stratified by region (Asia, rest of world).

For Part 2, eligible subjects will not be randomized, but will instead be registered in IXRS.

Once the subject is randomized, first dose / Cycle 1 Day 1 should occur within 7 days from the randomization date.

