11. STATISTICAL METHODS

11.1. Analysis Sets

11.1.1. Full Analysis Set/Safety Analysis Set

The Full Analysis Set (FAS)/Safety Analysis Set will include all subjects enrolled in Part 1 or Part 2 who received at least one dose of study drug.

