11.2. General Statistical Considerations

A data cut-off date for the primary analysis will be identified during Part 2.

Data in Part 1 and Part 2a will be combined by the starting dose level. Summary statistics will be presented by part/dose group. Continuous variables will be summarized by the number of observations, mean, standard deviation, median, minimum, and maximum values. Categorical variables will be summarized using frequency counts and percentages.

Assessments of change from baseline to post-treatment or the ratio of post-treatment to baseline will include only those subjects with both baseline and post-treatment measurements. The last non-missing value of a variable taken before the first dose of study treatment will be used as the baseline value, unless otherwise specified. In general, missing or dropout data will not be imputed for the purpose of data analysis, unless otherwise specified.

Analyses of ORR, DCR, and CBR will be performed on the Response Evaluable Set. The other efficacy analyses will be performed on the Full Analysis Set (FAS). Safety analyses will be performed using the Safety Analysis Set. Analysis of PK parameters will be based on the PK Analysis Set. All other exploratory analyses will be performed based on the FAS and availability of assessment.

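### PFS and OS are timed from randomization/registration but analysed only in dosed subjects, so each time includes a short interval before first dose in which no analysed subject can die

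*Combined protocol and SAP*

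**What the plan says.** For PFS, Section 11.4.1.2.2 reads "PFS is defined as the time from the date of randomization/registration to the earlier of the dates of the first objective documentation" and goes on to name centrally reviewed radiographic progression or death. For OS it reads "OS is defined as the time from the date of randomization/registration to the date of death for any cause". Section 11.2 assigns all efficacy analyses other than ORR, DCR and CBR to the Full Analysis Set (FAS). Under Section 11.1.1 that set "will include all subjects enrolled in Part 1 or Part 2 who received at least one dose of study drug". Section 5.7.4 adds that "it is allowable to replace a subject that was enrolled but was not administered any study medication".

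On the interval between the two dates, Section 6.3 states "Once the subject is randomized, first dose / Cycle 1 Day 1 should occur within 7 days from the randomization date", and Section 3.1.3 says the same. Section 6.3 also states "For Part 2, eligible subjects will not be randomized, but will instead be registered in IXRS". No sentence sets a limit from registration to first dose.

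Three other places bear on the point. Section 6.4.2 counts the six-weekly scans from Cycle 1 Day 1. Section 6.2 puts most screening assessments, including the eligibility review, in the 14 days before first dose, and the screening column of Table 6.2, which covers Part 2, carries the same window. Section 4 treats a subject as enrolled only once consent is given and all eligibility criteria are met.

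**The concern.** Membership of the FAS is decided at first dose, after the PFS and OS clocks have started. A subject who dies while waiting for the first dose does not become an early event; the subject leaves the analysis and may be replaced. Every subject who stays is credited with the waiting time. This is immortal time, and it can only lengthen the reported times. The endpoint clock and the scan clock also have different zeros.

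At stake are the PFS and OS medians for a treatment with no control arm. The wait may differ between parts, because the written 7-day statement names randomized subjects, while 100 of the 150 subjects planned at the recommended dose come from Part 2a and are registered.

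**Working it through.** **The plan's own figures.** The documents state no design figure for PFS or OS. The sample-size figures in Section 11.6 concern ORR, with n = 150 and true ORR 35%. The smallest responder count whose exact lower 95% bound exceeds 20% is 41, and P(X ≥ 41) = 98.16% (stated 98.2%). ORR of at least 30% means 45 responders, and P(X ≥ 45) = 91.59% (stated 91.6%). Both reproduce, and neither depends on the time origin.

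**Length of the interval.**

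1. Part 1 (randomized): at most 7 days, if Sections 3.1.3 and 6.3 are followed. Both say should.
2. Part 2 (registered): the eligibility review falls within 14 days before first dose (Section 6.2), and enrolment requires that review to be complete (Section 4). If registration follows the eligibility decision, it comes no earlier than 14 days before first dose. This limit is inferred. It could be passed if the screening tests and the review were repeated after registration.

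**Effect on the median.** If every dosed subject waits g days, each time from registration equals the time from first dose plus g, so the median moves by exactly g. If waits vary between 0 and g, the underlying median moves by no more than g. In months, g / 30.4375:

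- 7 days: 7 / 30.4375 = 0.23 months
- 14 days: 14 / 30.4375 = 0.46 months
- 150 subjects at the maximum waits: (50 × 7 + 100 × 14) / 150 = 11.7 days = 0.38 months

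The documents give no median, so 6, 9 and 12 months are assumed:

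| Assumed median | 7 days | 14 days |
|---|---|---|
| 6 months | 3.8% | 7.7% |
| 9 months | 2.6% | 5.1% |
| 12 months | 1.9% | 3.8% |

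**A less extreme case.** The wait is taken as uniform on 0 to 14 days, with exponential event times from registration and subjects dropped if the event precedes dosing (2,000,000 simulated subjects per row; medians in months):

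| Assumed median | All registered, from registration | Dosed only, from first dose | Dosed only, from registration (the plan) | Lost before dosing |
|---|---|---|---|---|
| 6 | 6.00 | 6.00 | 6.23 | 2.60% |
| 9 | 9.01 | 9.01 | 9.24 | 1.75% |
| 12 | 11.99 | 11.99 | 12.22 | 1.31% |

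Under a constant hazard, the two pairings in which origin and analysis set agree give the same median. The plan's mixed pairing is about 0.23 months longer.

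**Sensitivity.** If the 14-day window were not enforced and every wait reached 28 days, the shift would be 28 / 30.4375 = 0.92 months.

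**The case against.** Much of the case on the other side stands.

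- **A reader might infer that the Part 2 interval has no limit.** The documents do not support that. The 14-day screening window, read with the enrolment definition in Section 4, limits it indirectly.
- **A reader might infer that the 7-day statement excludes Part 2.** That is not settled. In Section 6.3 it comes directly after the sentence on Part 2 registration, and footnote c of Table 6.2 uses randomization alone in a table that covers Part 2. On the other hand, the exclusion criteria, the screening windows and the endpoint definitions name both events. This is an ambiguity to reconcile.
- **Part of the shift is only an earlier, disclosed origin in a non-comparative estimate.** This is fair. The selection element is the loss of early events. No follow-up scan is scheduled before dosing, so these would be essentially deaths, in subjects with ECOG status 0 or 1, over days. The simulated losses of 1.31% to 2.60% apply a constant PFS hazard to a scan-free interval and are probably too high.
- **The percentages depend on the assumed median.** Section 3.1.3 expects most subjects to receive 10 to 20 cycles, that is 210 to 420 days. If that is a rough proxy for PFS, 14 days is 14/210 = 6.7% down to 14/420 = 3.3%. For OS the share would be smaller.
- **The consequences are low.** PFS and OS are secondary, descriptive medians with no test. ORR and duration of response do not use this origin. Section 11.3 already tabulates disposition and analysis sets.

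None of this removes the mismatch between the origin and the analysis set.

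**Conclusion.** The mismatch is real and small. As written, each PFS and OS time includes an interval before first dose in which no FAS member can die. The medians are lengthened by at most about 0.23 months at 7 days or 0.46 months at 14 days, and by 0.38 months on average over the 150 subjects if every wait is at its maximum. A reader might take this as a threat to the main result; it is not, because primary ORR has no such origin.

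The sizes rest on three assumptions: the 7-day statement is followed in Part 1, registration follows the eligibility decision in Part 2, and the median is 6 to 12 months. The numbers registered but not dosed are not given. The protocol leaves censoring rules for PFS to the SAP, but it fixes the origin itself, and the combined file as read contains no SAP wording that changes it. The priority is minor: a cheap improvement.

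**What to change.** Define PFS and OS from the date of first dose. This matches the dosed-only FAS and the Cycle 1 Day 1 scan clock. The cost is a wording change in Section 11.4.1.2.2, one derivation, and slightly shorter medians.

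The change of origin does not bring back subjects lost before dosing. Therefore report, by part, the number randomized or registered but never dosed, with the reasons, and the distribution of the interval to first dose. The other coherent choice is to keep the present origin and include all randomized or registered subjects in PFS and OS, which would need a further analysis set.

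Reconcile Sections 3.1.3 and 6.3 so that they say whether the 7-day statement also covers registered Part 2 subjects.

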5.7. Removal of Subjects From Treatment and/or Study

5.7.1. Reasons for Discontinuation of Study Treatment

Subjects may be withdrawn from study treatment after signing informed consent for the following reasons:

- Progressive disease per criteria set forth in RECIST version 1.1;
- Clinical progression (definitive clinical signs of (PD), but a recent radiographic assessment did not meet the criteria for Progressive Disease according to RECIST version 1.1);
- Adverse event;
- Withdrawal of consent by subject;
- Physician Decision;
- Death;
- Pregnancy;
- Study terminated by Sponsor;
- Lost to follow-up;
- Other, specify.

If there is evidence that the subject is receiving benefit from treatment even though the subject has met a criterion for discontinuation as listed above, the subject may remain on study treatment after discussion with the Global Clinical Lead.

All subjects who are withdrawn from study treatment should complete protocol-specified withdrawal procedures (Section 5.7.3) and follow-up procedures (Section 6.6).

Record the reason for any subject who discontinues study treatment. Discontinued subjects will be followed for survival, either through direct contacts or by collecting public records (eg, death certificates) as allowed by local laws.

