5.7.2. Reasons for Discontinuation of Study Participation

- Subject withdraws consent to participate in study procedures;
- Subject dies;
- Study is terminated;
- Subject is lost to follow-up;
- Other, specify.

Note: All subjects will be followed for survival status even after consent for study procedures is withdrawn. Subjects discontinued from the study because of withdrawal of consent will be followed for survival by collecting public records (eg, death certificates) every 3 months from the last study visit, unless prohibited by local laws.

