6.6. Follow-up

Forty days (+7 days) after last study drug administration or before starting new anticancer treatment, whichever comes first, the following procedures will be performed as specified in the Schedule of Events. If EOT is > 40 (+7) days after last treatment, then the EOT assessments can also function as the follow-up visit.

- Vital signs (systolic and diastolic blood pressure, pulse rate, respiratory rate, body temperature and SpO₂).
- Physical examination. Weight will be recorded.
- ECOG PS.
- Hematology, blood chemistry, and troponin assessments will be performed.
- AEs and concomitant medications will be recorded.
- For subjects with positive ADA at the follow-up visit, additional serum ADA samples must be collected every 3 months (\pm 1 month) up to 1 year from the last dose of study drug, or until the ADA becomes negative, or until the ADA titer becomes less than baseline (applicable when pre-existing ADA is observed), or until the subject starts another therapy for cancer, or withdraws consent from the study, whichever occurs first.

Subjects will also be assessed every three months (\pm 14 days), from the date of follow-up visit, for survival and subsequent anticancer therapy until death, withdrawal of consent, loss to follow-up, or study closure; whichever occurs first. This information may be collected in a visit or via phone contact, or (as necessary for survival status, in the case of withdrawal of consent or loss to follow-up) from public records as allowed by law.

Further follow-up may be required for ongoing AEs (see Section 9.1).

Table 6.1: Schedule of Events – Part 1 PK Stage

	Tissue Screen	S C R (-14 d or as not ed)	Cycle 1					Cycle 2			Cycle 3			Cycle 4 and subsequent cycles		Every 6 wks (±7 days)	EOT (a)	40-day FU (±14 days)	q3 mo FU (±14 days)					
			Day 1		Day 2	Day 4	Day 8	Day 15	Day 22 ^v	Day 1		Day 22 ^v	Day 1		Day 22 ^v									
			BI	EOI			(±1 day)	(±1 day)	(±2 days)	BI	EOI	(±2 days)	BI	EOI	(±2 days)					BI	EOI			
Informed Consent (may sign)	•	•																						
Administer DS 8201a			•						•			•			•									
Medical		•																						
Demograp		•																						
Pregnancy		•																	•					
Vital Signs		•	•	•		•	•		•	•		•	•		•			•	•					
Physical		•	•						•			•			•			•	•					
SpO2		•	•						•	(d)		•	(d)		•	(d)		•	•					
Inclusion/Exclusion		•																						
Height		•																						
Weight, ECG, BP		•	•						•			•			•			•	•					

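### Withdrawn or lost subjects are observed beyond last contact only if public records show a death, so OS censoring depends on the outcome; a symmetric sensitivity analysis is needed

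*Combined protocol and SAP*

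**What the plan says.** Section 11.4.1.2.2 defines the event without limiting how a death is learned: "OS is defined as the time from the date of randomization/registration to the date of death for any cause". For a subject with no reported death before the cut-off, "OS will be censored at the last contact date at which the subject is known to be alive". The planned summary is the median: "Duration of response, PFS, and OS will be summarized with median event times and their 2-sided 95% CI for the median".

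Three places let deaths be found without contact:

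- Section 5.7.2, after withdrawal of consent: such subjects "will be followed for survival by collecting public records (eg, death certificates) every 3 months from the last study visit, unless prohibited by local laws".
- Section 6.6, long-term follow-up, which extends this to lost subjects: "as necessary for survival status, in the case of withdrawal of consent or loss to follow-up) from public records as allowed by law".
- Section 5.7.1, after stopping treatment: survival is followed "either through direct contacts or by collecting public records (eg, death certificates) as allowed by local laws".

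No section credits the time up to a search that finds no death, and none restricts OS events to deaths known by last contact. Section 11.4.1.2.2 leaves the censoring detail for duration of response and PFS to the SAP, but it states the OS rule itself.

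**The concern.** Take two subjects who withdraw on the same day. One dies five months later and the death certificate is found: that subject stays at risk for those five months and then counts as an event. The other is alive at the cut-off. A death-certificate search that finds nothing creates no contact, so that subject is censored at withdrawal. After last contact, only the subjects who die are seen.

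A Kaplan-Meier median is valid only if being followed at a given time does not depend on the outcome. Here deaths enter without the matching survival time of the subjects who did not die. OS is a named secondary endpoint, and Section 11.4.1.3.1 also analyses it by region. Record searches are made only where local law allows, so the effect can differ between countries.

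**Working it through.** **The plan's own figures.** None are given for OS, for loss or withdrawal, or for the completeness of the record search. The only sizing figures (Section 11.6) concern ORR with 150 subjects at a true rate of 35%, and they reproduce. A lower exact 95% bound above 20% needs at least 41 responders, probability 0.9816 (stated 98.2%). An observed ORR of at least 30% needs at least 45, probability 0.9159 (stated 91.6%). Neither bears on OS.

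**Direction against symmetric rules.** The Kaplan-Meier estimate is S(t) = product of (1 − d/n) over death times up to t. Two rules treat both outcomes alike:

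- *Rule A:* found deaths count, and subjects with no death found are censored at the search or cut-off date.
- *Rule B:* all withdrawn or lost subjects are censored at last contact, and deaths learned only later from records do not count.

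Against Rule A the planned rule has the same d and an equal or smaller n at each death time, so its curve can never be higher. Against Rule B it adds back only subjects who will die before the cut-off C. If loss is unrelated to prognosis, their hazard is h(t) / [1 − S(C)/S(t)], which exceeds h(t). With an assumed 15-month median, h = ln 2 / 15 = 0.0462 per month. With 10 months left, S(C)/S(t) = exp(−0.462) = 0.63, and the hazard is 0.0462 / 0.37 = 0.125, about 2.7 times too high for those subjects.

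**Size: simulation.** From Section 3.1.2: 12-month accrual and at least 10 months of follow-up. Assumed, because the documents are silent: exponential OS, the loss rate and timing, the share of deaths found, and the hazard after loss.

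*Median 15 months; loss times uniform over 0–9 months:*

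| Lost alive | Deaths found | Hazard after loss | Planned | True | Planned − true |
|---|---|---|---|---|---|
| 4% | all | ×1 | about 14.6 | 15.0 | about −0.4 |
| 8% | all | ×1 | 14.25 | 15.0 | −0.75 |
| 8% | half | ×2 | 14.35 | 14.22 | +0.13 |
| 8% | half | ×3 | 14.15 | 13.71 | +0.44 |

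*Median 18 months before any change in hazard; loss times uniform over 0–12 months:*

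| Lost alive | Deaths found | Hazard after loss | Planned | True | Rule A | Rule B |
|---|---|---|---|---|---|---|
| 4% | all | ×1 | 17.5 | 18.0 | 18.0 | 18.0 |
| 8% | all | ×1 | 17.0 | 18.0 | 18.0 | 18.0 |
| 16% | all | ×1 | 16.1 | 18.0 | 18.0 | 18.0 |
| 8% | all | ×2 | 16.5 | 17.1 | 17.1 | 18.0 |
| 8% | half | ×1 | 17.6 | 18.1 | 18.9 | 18.1 |
| 8% | half | ×2 | 17.2 | 17.1 | 18.3 | 18.0 |
| 8% | half | ×4 | 16.8 | 16.2 | 17.7 | 17.9 |

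The planned median is below both symmetric rules in every row. Against the truth it is low with a complete search, and low with a half-complete search if loss is unrelated to prognosis. It is near the truth or high when half the deaths are missed and mortality after loss is raised.

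**The case against.** A reader might infer that OS in this trial is simply biased downward. The documents do not support that. The statement needs a near-complete search or loss unrelated to prognosis, and neither is stated. Because searches are limited by local law, completeness is doubtful. Missed deaths push the other way and can outweigh the effect, as the last row of each table shows. This part of the objection stands.

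A reader might also infer that the main rule should be replaced by censoring at the last negative search. That can be worse than the plan. With a 15-month median, a half-complete search and loss unrelated to prognosis, it gave 15.79 months against a true 15.06. A negative search is not proof of life. Dropping later deaths (Rule B) overstates OS when mortality after loss is raised. In an uncontrolled trial, either error flatters the drug. This stands too.

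The size is modest. A shift of about 0.75 months lies well inside the 95% sampling range of the median with 150 subjects, about 11.7 to 19.3 months. Sections 3.1.3 and 6.6 also provide for three-monthly contact, which may keep losses few. But sampling error shrinks with more data and is shown by the confidence interval; this error is neither.

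Death certificates are only the example given, and the date of last contact is not defined. A source that positively confirms life could supply a later date and shrink the effect, but a death-certificate search cannot. Section 11.7 leaves definitions to a SAP. The combined document holds no SAP text that changes the OS rule, so a repair there cannot be assumed or excluded.

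**Conclusion.** The asymmetry is real: it follows from Sections 5.7.2, 6.6 and 11.4.1.2.2 read together, and no other section corrects it. The planned OS estimate lies below symmetric rules, by arithmetic for Rule A and in every scenario run for Rule B. Its error against true OS has no fixed sign.

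The size rests on assumed figures. With exponential OS, a 15-month median, a complete search and loss unrelated to prognosis, the median is about 0.4 months low with 4% lost alive (6 of 150) and 0.75 months low with 8% (12 of 150).

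The consequence is limited. OS is secondary and descriptive, no OS test or sizing depends on it, and ORR is untouched. A regional difference in OS caused by differing searches is possible, but nothing in the documents shows that one will occur. The point merits a sensitivity analysis and better data capture, not a new main analysis.

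**What to change.** Keep the planned rule as the main OS analysis unless record searches are known to be complete. Then:

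1. Add to Section 11.4.1.2.2 a sensitivity analysis that censors all withdrawn or lost subjects at last contact and does not count deaths learned only from later record searches.
2. Where a registry is known to be complete, add a second analysis that censors subjects with no death found at the date through which the registry is complete, and never after the data cut-off.
3. Record the date of each record search.
4. Report the number of OS events found only in public records, by region.

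The gap between the analyses shows how far OS depends on record-only deaths. It need not bracket the truth: with half the deaths found and a fourfold hazard after loss, the planned rule (16.8 months) and Rule B (17.9) both exceed the true 16.2. The report should say so.

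The cost is a short addition to the text, one data field and a little extra analysis, with no added visits.
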